EMRs of current smokers should be reviewed for patients who are adult ( $\geq 18$  years) and newly diagnosed (within past 4 months). Site staff should then approach these patients to confirm smoking status, receipt of care at the NCORP site, and email/web access, as well as any above-listed criteria that were unable to be discerned from chart review.

Only patients who are still eligible after this initial chart review step should be approached about the study. For patients who are deemed ineligible, or whom refuse to be fully screened upon approach, during this screening process, site staff will document reasons in the MSK REDCap Survey (see Section [5.1.1](#)).

For patients who meet study criteria, the site staff will ask the patient if it is okay for central coordinating study staff to contact them with a brief, informational video about the study. Verbal permission may occur per sites usual practice (via telephone or in clinic). For patients who refuse, reasons for refusal will be documented and tracked in the study specific enrollment log. Patients who agree to be contacted about the study will be registered in OPEN (Screening Step 0). Patient contact information and screening characteristics (criteria collected above) will be entered into OPEN. Once a Patient's information is in OPEN, the virtual clinician referral (informational video) will be sent to the email address provided by EASEE PRO. It is highly recommended that site staff have an interested and eligible participant view the video at the time of visit and then also obtain written consent (OPEN Step 1).

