Participants may choose to wait to sign consent, but give verbal consent to view the outreach recruitment video. Site staff will then follow-up with all patients who received a virtual clinician referral to assess their interest in participating in the study. Additionally, EASEE-PRO will prompt site staff when a patient has watched the virtual clinician referral video, to help facilitate recruitment efforts. Follow-up attempts may occur at upcoming clinic visits or via phone. It is recommended site staff make at least 3 outreach attempts (e.g., approaches in clinic, or voicemails), unless a refusal or enrollment decision is received first. For those who refuse or are ineligible for the study, reasons will be documented in RAVE and ongoing secure data transfers will be sent to MGH. Otherwise, interested, eligible patients will be given an informed consent form to review and sign, and will be consented to the study by the NCORP site staff.

Once a patient has signed written consent, they will be registered to OPEN Step 1 of the study and be prompted to complete the Baseline Survey in EASEE-PRO. After completion of the Baseline Survey, the patient will then be eligible to register to OPEN Step 2 of the study, which will randomize them to a treatment arm. Following OPEN Step 2, NCORP site staff will send patient contact information, study ID, dates of consent and randomization, provider information, and randomization arm assignment to MGH centralized study staff via the site's Enrollment Log REDCap project. MGH site staff will then email participants' provider an email notification of enrollment in the study.

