Rev. Add3	
9.8.2.2 Adoption
 
Using the baseline, 12- and 36-month staff surveys, we will conduct paired t-tests and chi-square test to assess pre/post changes in organizational readiness (ORIC) and tobacco treatment delivery practices.

Rev. Add4	
9.8.2.3 Appropriateness
 
To measure perceived fit and relevance, we will report on the 12- and 36-month staff surveys and interviews of NCORP PIs, clinicians, and staff about the VIT's a) suitability, b) applicability, and c) match for their patients and site, as well as d) perceptions of site usual care content and implementation.

Rev. Add2	
9.8.2.4 Fidelity
 
We will evaluate the use and effectiveness of brief videos on enrollment using the Fisher's exact test: brief videos open (y/n) and enrollment (y/n). Using participant self-reported survey data, counselor process data, and quitline data, we will evaluate study treatment and non-study treatment (i.e., site-specific usual care, outside resources) utilization. We will dichotomize medication and counseling use into low vs. high (<math>\geq 8</math> weeks of NRT; <math>\geq 8</math> sessions) levels of treatment utilization. Within each group, we will use chi-square tests and ANOVAs to explore the association between participant characteristics and treatment utilization. We will use chi-square tests to compare the association of treatment utilization (brief videos open, level of medication and counseling use) on smoking outcomes. To predict smoking outcomes, we will use logistic regression models, which will include medication and counseling use levels, adjusting for confounders.

	
9.8.2.5 Cost

Rev. Add2  
Rev. Add3

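### Section 9.8.2.4 reads an opened-by-enrolled table as the effectiveness of the recruitment video, but the recruitment procedure in 5.1 mixes prior interest and prompted staff effort into that table

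*Combined protocol and SAP*

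**What the plan says.** Section 9.8.2.4 (Fidelity) states: "We will evaluate the use and effectiveness of brief videos on enrollment using the" Fisher's "exact test: brief videos open (y/n) and enrollment (y/n"). The only adjustment in that section belongs to the models for smoking outcomes, "which will include medication and counseling use levels, adjusting for confounders". It does not reach the video test.

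Section 5.1 describes how patients come to open the video:

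- Once a patient is entered at Step 0, the video goes to the e-mail address on file, so every Step 0 patient is sent it.
- "It is highly recommended that site staff have an interested and eligible participant view the video at the time of visit". The sentence continues "at the time of visit and then also obtain written consent (OPEN Step 1").
- "EASEE-PRO will prompt site staff when a patient has watched the virtual clinician referral video, to help facilitate recruitment efforts".
- "Site staff will then follow-up with all patients who received a virtual clinician referral to assess their interest", with at least three attempts recommended.

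Section 6.5 has central staff record the percentage of videos opened. Section 5.1.3 gives the delivery route as the site's patient portal, not e-mail.

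**The concern.** Effectiveness on enrollment is a causal claim, and the planned table cannot isolate a causal effect. Three features of 5.1 stand in the way:

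- Interest can come before viewing. A patient shown the video in clinic has been picked because of willingness and is then asked to sign, so that patient tends to land in the opened-and-enrolled cell whatever the video does.
- Viewing can cause recruitment effort. Anything the staff prompt achieves is credited to the video.
- Everyone at Step 0 is sent the video, so the non-openers are self-selected and are not an unexposed group.

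No section orders opening before consent, separates in-clinic from remote views, or adjusts this test. What is at stake is one implementation conclusion. Section 1.1 lists brief clinician videos among the ways the trial improves reach, and the implementation data are meant to inform later dissemination work. A small p-value under the label of effectiveness would say more than the design allows.

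**Working it through.** The plan gives no sample size, significance level or expected rates for this test, so there is no figure to reproduce. The check asks what the test shows when the video has **no** effect.

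**Inputs from the documents.** 308 enrolled (9.4). Enrollment fractions from the team's earlier trial (1.2.1): 70% of known eligible smokers who agreed to screening, and about one-third of those potentially eligible on chart screen. If these carry over (an assumption), the table holds 308/0.70 = 440 or 308 × 3 = 924 patients.

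**Assumed, because the documents are silent.**
- *e*: share who would enroll anyway (0.70 or 1/3).
- *q*: chance of opening the e-mailed video, equal for willing and unwilling patients (0.3, 0.5, 0.7).
- *f*: share of willing patients shown the video in clinic before consent, logged as opened.
- *δ*: extra enrollment among openers due only to the staff prompt.

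**1. In-clinic viewing alone (δ = 0).** Willing patients open with probability f + (1−f)q, unwilling patients with probability q. The odds ratio is

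{[f + (1−f)q] / [(1−f)(1−q)]} ÷ {q/(1−q)} = 1 + f/[(1−f)q].

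At f = 0.25, q = 0.5 this is 1 + 0.25/0.375 = 1.67. With 440 patients, the 308 willing split 192.5 opened and 115.5 not, and the 132 unwilling split 66 and 66. Openers enroll at 192.5/258.5 = 74% and non-openers at 115.5/181.5 = 64%.

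Share of 1,000 simulated trials per scenario with Fisher p < 0.05 (two-sided) in the positive direction, over the three values of q:

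| f | Odds ratio at q = 0.3 / 0.5 / 0.7 | N = 440 | N = 924 |
|---|---|---|---|
| 0 | 1 / 1 / 1 | 2.2–2.8% | 1.7–2.4% |
| 0.10 | 1.37 / 1.22 / 1.16 | 8–27% | 12–56% |
| 0.25 | 2.11 / 1.67 / 1.48 | 40–93% | 65–100% |
| 0.50 | 4.33 / 3.00 / 2.43 | 92–100% | 100% |
| 0.80 | 14.3 / 9.0 / 6.7 | 100% | 100% |

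**2. Staff prompt alone (f = 0).** Odds ratio = [(e+δ)/(1−e−δ)] ÷ [e/(1−e)].
- δ = 0.10: (0.80/0.20)/(0.70/0.30) = 1.71 at e = 0.70, and (0.433/0.567)/(0.333/0.667) = 1.53 at e = 1/3. Significantly positive in 57% to 87% of runs.
- δ = 0.05: 1.29 and 1.24, positive in 17% to 36%.
- f = 0.25 and δ = 0.05 together: positive in 73% to 100%.

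**3. In-clinic views not logged as opened.** Willing patients then count as openers with probability (1−f)q. At f = 0.25, q = 0.5 the odds ratio is (0.375/0.625)/(0.5/0.5) = 0.60, and no run was significantly positive.

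**4. Remote opening that depends on interest.** Steps 1 to 3 assume it does not. Suppose half the patients are interested, enrollment is 60% vs 30% and opening 70% vs 40% by interest (assumptions). Openers enroll at (0.5×0.7×0.6 + 0.5×0.4×0.3)/0.55 = 49%, non-openers at (0.5×0.3×0.6 + 0.5×0.6×0.3)/0.45 = 40%. The odds ratio is 1.45, significantly positive in about 45% of runs at N = 440. With a stronger link (enrollment 70% vs 20%, opening 80% vs 30%) the figures are 56% vs 31% and an odds ratio of 2.86.

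**The case against.** The strongest reply is that a reader might infer a certain false positive, and the documents do not support that. In-clinic viewing is highly recommended, not required, and its uptake is unknown; at 10% uptake the false-positive rate is 8% to 56%. Staff are to follow up every referred patient, which weakens the prompt mechanism, though not the in-clinic one. The documents do not say how an in-clinic view is logged, and step 3 shows that the direction depends on it. All of this stands. It limits what can be said about sign and size, but it does not make the table a measure of effectiveness.

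A reader might also infer damage to the trial's main comparison. There is none: the video comes before randomization, both arms receive it, and the test is one exploratory item under Aim 3, which seeks an initial understanding of implementation. Nor does any section commit the team to disseminating the videos on this result, so that consequence is a possibility only.

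Finally, Section 6.5 already records opening as a fidelity measure. That is correct, and it makes the remedy cheaper.

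**Conclusion.** The point holds as a limit on interpretation. The opened-by-enrolled association mixes any video effect with prior interest and prompted staff effort, and it cannot support a statement about effectiveness. It can look strongly positive for a video that does nothing: if half or more of the willing patients view in clinic and those views are logged, the test is significantly positive in at least 92% of runs. It can be biased the other way if those views go unlogged. The sizes rest on assumed values of *f*, *q* and *δ* and on the earlier trial's enrollment fractions. The conclusion that the test does not identify a video effect rests only on 5.1 and 9.8.2.4. Importance is low: the analysis is exploratory, and the primary endpoint is unaffected.

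**What to change.** In 9.8.2.4, delete the word *effectiveness*, report video opening as a delivery or fidelity measure, and label any opened-by-enrolled comparison an association that includes prior interest and staff follow-up triggered by opening.

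If the comparison is kept:

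- Record the place and date of first viewing when it happens. A field at Step 0 is too early, because the video is sent after Step 0 entry.
- Exclude **all** in-clinic viewers, whether or not they consented. Dropping only those who consented the same day would condition on the outcome. For example, let 25% of all patients view in clinic regardless of willingness, 80% of the willing viewers sign that day, and half of e-mailed videos be opened (assumptions). A video with no effect then gives (0.05 + 0.375)/0.375 ÷ (0.25 + 0.375)/0.375 = 0.68. Excluding every in-clinic viewer returns 1.0 in that model.
- Count only remote opens dated before written consent. As step 4 shows, the result is still an association.
- State which step counts as enrollment.

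Reconcile the delivery route between 5.1 (e-mail) and 5.1.3 (patient portal), so that *opened* has one meaning.

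The cost is a wording change, one extra data item for place and date of viewing, and a smaller, less favourable comparison. If data collection can no longer change, the wording change alone removes the unsupported claim.

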
### 1.2.1 Current R01 preliminary findings (Smokefree Support Study 1).

The proposed study was informed by the recently completed RCT which Drs. [name] and [name] conducted at MGH and Memorial Sloan Kettering (MSK) to assess integration of an Intensive Treatment (IT; 11 sessions of motivational counseling, in-person and phone, plus choice of FDA-approved medication) versus MSK's usual care with recently diagnosed cancer patients (4 sessions of MI counseling plus FDA-approved medication advice). Among patients who are potentially eligible based on chart screen, approximately one-third enrolled; among known eligible smokers who agreed to be screened, 70% enrolled. Based on preliminary analyses as of February 2018, 303 patients were enrolled and randomized to a treatment arm (56%

female, mean age = 58; 82% white, non-Hispanic; 10 % Black; 5.0% Hispanic). This includes patients diagnosed with thoracic, head and neck, GI, GU, breast, lymphoma, melanoma, and ob/gyn cancers. Using intention-to-treat analyses counting non-responders as "smokers" (86% 6-month survey response rate and 87% cotinine validation response rate), cotinine validated 6-month abstinence rates are 19% in the Standard Care group and 33% in the Intensive Treatment group ( $p < .02$ ). Using intention-to-treat, 57% of Intervention Treatment group participants were adherent to sustained counseling (> 7 sessions), which was associated with increased 6-month quit rates ( $p < .0001$ ). These data support preliminary effectiveness of the proposed intervention treatment.

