### 5.3 Virtual Intervention Treatment (VIT) (Arm B)

The VIT group will be offered up to 11 counseling sessions over approximately 6 months (approximate schedule: 4 weekly sessions through week 4; 4 biweekly sessions through week 12; and 3 monthly sessions through week 24) and up to 12 weeks of free FDA-approved combination NRT (patch and lozenge combined, or may elect to receive either option alone).

VIT participants will receive their 11 counseling sessions via MGH TeleHealth, which connects providers to patients through virtual HIPAA-compliant videoconferencing technology including: phone, video, email, mobile applications and remote monitoring. These virtual visits are conducted via a videoconference platform that addresses clinical privacy and security (e.g., Zoom, Doximity, or other HIPPA-compliant platform). Participants can use this videoconference platform on their computer, tablet or smartphone. The counseling will be delivered by a study-designated tobacco treatment coach based at MGH. Since the counseling takes place virtually, participants will be emailed handouts that are traditionally provided as hardcopies in person. These handouts, distributed at the end of Session 1, include a pill diary, 11 Reasons for Cancer Patients to Quit Smoking, and Health Benefits When You Quit Smoking.

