## 9. Statistical Considerations

### 9.1 Estimated Effect Size

Based on our current trial preliminary findings (Preliminary Studies) and previous trial with low SES smokers, we conservatively estimate 7-day point-prevalence tobacco abstinence at 6-month follow-up will be 15% for the standard care group and 32% for the intervention group. This estimate is based on our current trial, which has a higher intensity control group.

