### 9.2 Power calculation:

#### 9.2.1 Aim 1. Primary effectiveness outcome.

The study will have 80% power to detect a 17% difference in 7-day point-prevalence tobacco abstinence with a two-sided significance level of 0.01 with 280 participants.

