For continuous abstinence, with a sample size of 140 in each arm then smallest detectable difference will be 21% with 80% power and a Bonferroni corrected alpha of 0.002 using and an estimated control rate of 20%.
- 9.2.6 Aim 1. Secondary effectiveness outcome 5.  
For sustained abstinence, with a sample size of 140 in each arm then smallest detectable difference will be 19% with 80% power and a Bonferroni corrected alpha of 0.002 using and an estimated control rate of 13%.
- 9.3 Estimate of drop-outs/loss to follow-up:  
We estimate that 10% of participants will die within 6-months of enrollment, so an additional 10% (n=28) will be recruited.
- 9.4 Total Sample size:  
308 patient participants.
- 9.5 Plans for handling missing data:  
At the outset, we will examine the frequency distributions of all variables. Data from all sites will be pooled for analysis, after confirming there is no significant heterogeneity among sites or adjusting as needed. We will compare the baseline characteristics to assess whether randomization distributed covariates evenly. Outcome analyses will be intent-to-treat; we will classify participants who are lost to follow-up and those who do not provide a saliva or an expired air sample as current smokers. We will determine whether there is differential dropout in the groups and consider developing probability-of-completion weights to obtain unbiased estimates of treatment effect. We will assess whether data are missing at random. We will perform sensitivity analysis using: 1) a complete case analysis and 2) multiple imputation for missing data.

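### The exploratory use-and-quitting analysis (9.8.2.4) can link high use to quitting when no relation exists, because missing patients count as smokers and use has no counting window

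*Combined protocol and SAP*

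**What the plan says.** Section 9.8.2.4, part of exploratory Aim 3, will "dichotomize medication and counseling use into low vs. high". High means at least 8 weeks of NRT and at least 8 sessions. It then states: "We will use chi-square tests to compare the association of treatment utilization" with smoking outcomes. Logistic models follow, adjusted for confounders that are not named. The smoking outcomes in 2.2 and 2.3 are measured at 3 and 6 months. The section gives no period over which use is counted and no exception to the general scoring rule.

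That rule is in 9.5: "we will classify participants who are lost to follow-up", or who give no saliva or breath sample, as smokers. Sections 9.6 and 9.7 repeat it, and 9.7 treats a missing self-report in the same way. Section 9.5 also plans a check for differential dropout, possible completion weights, and complete-case and multiple-imputation sensitivity analyses.

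On timing, counseling in 5.3 ends with "3 monthly sessions through week 24". The schedule in 7.3 puts session 8 in week 10 (5.3 implies week 12), in the same row as the VIT 3-month follow-up. Sessions 9, 10 and 11 are in weeks 13, 17 and 21. Section 7.1 lets the 3-month survey run from 7 days before to 49 days after its target, and places the VIT 6-month survey after session 11 is closed out. Section 5.6 limits NRT to 12 weeks.

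**The concern.** Two features can each produce a link between use and quitting that has nothing to do with benefit.

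- **Scoring.** A patient who disengages or dies early tends to complete few sessions and is also likely to have no 6-month outcome. Coding that patient a smoker puts the same event on both sides of the test. Covariate adjustment does not undo a coding rule.
- **Timing.** With one split at 8 of 11 sessions and no window, a VIT patient who misses any of the first 8 can become a high user only through sessions 9 to 11, which are scheduled after the 3-month follow-up. If patients still smoking at 3 months attend fewer later sessions, the outcome influences the exposure.

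The trial could then report that sustained counseling predicts quitting when the finding is partly an artefact. Section 1.2.1 already cites such a result from the earlier trial: "57% of Intervention Treatment group participants were adherent to sustained counseling" (more than 7 sessions), associated with quitting at p<.0001 with non-responders counted as smokers.

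**Working it through.** **1. The plan's own figure.** The plan gives no calculation for the use analysis. For the primary comparison it has "The study will have 80% power to detect a 17% difference", "with a two-sided significance level of 0.01 with 280 participants", and assumes "15% for the standard care group and 32% for the intervention group". The unpooled formula gives n = (2.576 + 0.842)² × (0.32×0.68 + 0.15×0.85) / 0.17² = 139.5, so 140 per arm, as stated. Adding 28 for deaths gives 308, or 154 per arm.

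**2. Dropout, 6 months.** Inputs from the documents: 57% high users and 86% survey response, so 14% lost (both from the earlier trial, 1.2.1); 32% abstinent in VIT (9.1). I take the analysis within VIT. Abstinence among responders is 0.32/0.86 = 0.372, set equal in high and low users, so there is no true relation. With lost = smoker, the observed rate is 0.372 × (1 − loss). How loss divides between high and low users is my assumption; each split averages 14% (for example 0.57×0.05 + 0.43×0.26 = 0.14). False positives come from simulating the uncorrected chi-square at 0.05 with N = 154.

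| Loss, high / low users | Observed abstinence | Gap, points | OR | False positives |
|---|---|---|---|---|
| 14% / 14% | 32.0% / 32.0% | 0 | 1.00 | 5% |
| 10% / 19% | 33.5% / 30.1% | 3.3 | 1.17 | 7% |
| 5% / 26% | 35.3% / 27.5% | 7.8 | 1.44 | 17 to 18% |
| 0% / 33% (all loss in low users) | 37.2% / 25.1% | 12.1 | 1.77 | 36% |

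The last row is an upper bound; at 0.01 it gives 16%. With N = 140 the four false-positive rates are 5, 7, 16 and 33%.

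**3. Deaths.** Section 9.3 expects 10% to die within 6 months, and the scoring rule does not name them. Suppose they are kept as smokers and fall 2% / 21% (assumed; 0.57×0.02 + 0.43×0.21 = 0.10) on top of the 5% / 26% loss. The rates are 0.372×0.95×0.98 = 34.6% and 0.372×0.74×0.79 = 21.8%. The gap is about 13 points and false positives about 41%.

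**4. Timing, 3 months.** N = 140; 38% quit in VIT (the 20% control rate plus the 18-point detectable difference in 9.2.2), independent of use. Each patient has an attendance probability drawn from a beta distribution, (3.2, 1.2) or (6, 2.2), both assumed. Eight sessions fall by month 3 and three after it; high means at least 8 of 11. In these runs 56 to 73% of high users reach 8 only after month 3.

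| Later attendance, smokers relative to quitters (assumed) | Gap, points | False positives at 0.05 |
|---|---|---|
| 1 | 0 | 5% |
| 0.75 | 8 to 10 | 15 to 21% |
| 0.5 | 16 to 20 | about 50 to 68% |

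**5. Remedies.** When dropout alone acts, restricting to responders returns the test to 5%. When 3-month smokers also attend later sessions at 0.75 or 0.5 times the quitters' rate, the responder analysis still gives about 17% or 58%. Counting use only up to month 3 (illustratively, at least 7 of the first 8 sessions) among responders gives 4.6 to 5.5% in every scenario run.

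**The case against.** **The plan already covers part of this.** Section 9.5 provides complete-case and multiple-imputation analyses and a differential-dropout check. That stands for the dropout part, although 9.8.2.4 does not invoke them. They do nothing about timing.

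**The bias is conditional.** A reader might infer that the scoring rule creates the association by definition. It does not: equal loss keeps the 5% level, and the 36% case needs every lost patient to be a low user.

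**A much larger effect can be computed, but the design contradicts it.** A reader might multiply the 86% survey and 87% cotinine response rates in 1.2.1 to get 25% unverified, treat them all as low users, and reach false-positive rates above 90%. Samples are requested only from patients who report having quit (6.1.3, 7.1). The unverified share is nearer 0.14 + 0.86 × 0.428 × 0.13 = 19%, where 0.428 = 0.32/(0.86×0.87). A self-reported quitter without a sample has answered the survey and is not a dropout.

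**Complete case is not a clean remedy.** It drops quitters without a sample but keeps self-reported smokers. If high and low users return samples at 95% and 76% (assumed; about 87% overall), the null rates are 0.407/(0.407+0.572) = 41.6% and 0.325/(0.325+0.572) = 36.2%. The gap is about 5 points and false positives about 9%. This stands, and is a reason to allow multiple imputation.

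**Timing is inferred and narrow.** The plan does not say that later sessions count toward 3-month outcomes; this follows from a single split without a window. The problem is weak for NRT, which ends by week 12. At 6 months the VIT sessions precede the survey. The 49-day allowance also means that sessions 9 or 10 precede some 3-month surveys.

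**The work is exploratory.** The plan calls the result an association and nowhere says it will set a recommended amount of treatment. That limits the consequence but does not make the test valid.

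**Conclusion.** The concern holds in a conditional form. As written, 9.8.2.4 can produce a use-quitting association with no true relation. Through dropout, false positives run from 5% to an upper bound of 36% at 14% loss, depending on how loss divides between high and low users. Through timing, for counseling against 3-month outcomes (including the 3-month part of sustained abstinence), they are about 15 to 21% or 50 to 68% if 3-month smokers attend later sessions at 0.75 or 0.5 times the quitters' rate. The documents supply the 57%, 14%, 32%, 38% and 10% inputs or the figures behind them. The uneven loss and later-attendance ratios are assumptions; if neither imbalance occurs, the test keeps its level. A reader might infer that the trial's main result is in doubt. It is not: the randomized primary comparison and the total of 308 do not depend on this analysis.

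**What to change.** For the 9.8.2.4 analyses only:

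1. Make observed-outcome or multiply imputed results the main analysis, show missing = smoker beside them, and state how deaths are handled.
2. For 3-month outcomes, count only sessions and NRT weeks completed before that patient's own 3-month survey. Express sessions as a number or a proportion of those due: only 8 are scheduled by then, so the present cut would require perfect attendance. For 6-month outcomes, use through session 11 may be counted because the VIT survey follows it; a month-3 landmark can be an optional sensitivity analysis.
3. Report the results as associations.

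This is SAP wording and needs no new data. The cost is fewer patients or some imputation work. Ordinary adherence confounding, in which more motivated patients both attend and quit, remains.

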We will calculate the incremental cost per quit of the intervention relative to EUC over the 6-month follow-up period as follows: (total per-person costs of intervention – total per-person costs of EUC)/(cessation rate with the intervention – cessation rate with EUC ). Cessation rates will be based on the primary outcome. Statistical uncertainty in cost and effectiveness inputs will be incorporated into the incremental cost per quit comparisons using Monte Carlo simulation methods allowing us to determine whether these ratios are significantly different from zero and allowing us to assess the proportion of simulation outcomes above or below relevant thresholds. The robustness of the cost-effectiveness ratio estimates will be further examined in sensitivity analyses in which each parameter is varied, singly and in combination, through plausible ranges. We will also generate “best case” and “worst case” analyses. Using Wilcoxon rank sum tests and trend tests (Cochran-Armitage), we will explore patient and site characteristics associated with implementation outcomes. We will also collect cost data on EUC components including staff time required to assess smoking status and refer current smokers to this tobacco treatment trial.

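### Section 9.8.2.5 tests the simulated cost per quit against zero, which does not address cost-effectiveness, and gives no rule for draws in which VIT is less effective

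*Combined protocol and SAP*

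**What the plan says.** Section 9.8.2.5 (Cost) introduces the statistic thus: "We will calculate the incremental cost per quit of the intervention relative to EUC over the 6-month follow-up period as follows". The formula is the per-person cost difference divided by the difference in cessation rates. On the denominator it adds: "Cessation rates will be based on the primary outcome". Uncertainty in both costs and effects enters by Monte Carlo simulation, and the results are put to two uses:

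- a test, "allowing us to determine whether these ratios are significantly different from zero";
- a count, to "assess the proportion of simulation outcomes above or below relevant thresholds".

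The section adds sensitivity analyses, varying parameters singly and jointly, and best and worst cases. It names no threshold value. It does not say which side of a threshold is favourable, or how a draw with a zero or negative quit difference is classified. Net benefit, a cost-effect plane and an acceptability curve are not mentioned there or elsewhere. Cost is an implementation outcome under Aim 3, which Section 2.4 lists as exploratory.

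**The concern.** A cost-effectiveness ratio is judged against what a payer would spend per quit. A value of zero arises only when the two arms cost the same. VIT adds up to 11 counseling sessions and up to 12 weeks of free NRT (Section 5.3). EUC is advice plus a Quitline referral (Section 5.2). Equal cost is therefore not a plausible hypothesis, and rejecting it says nothing about value for money.

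The ratio also loses information when its sign can change. A negative value can mean cheaper and better, or dearer and worse. Both lie below any positive threshold. If the count is made on the ratio, the second kind joins the favourable side, and this happens most often when the effect is small or absent. The protocol presents the cost results as guidance for uptake in community oncology, so a misleading probability would matter most in that case.

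**Working it through.** **1. Reproduce the plan's own figure for the denominator.** The documents state no cost-effectiveness result, but the ratio's effect input is the primary outcome. Section 9.1 assumes 6-month abstinence "will be 15% for the standard care group and 32% for the intervention group". Section 9.2.1 claims "80% power to detect a 17% difference" at a "two-sided significance level of 0.01 with 280 participants". The unpooled Z formula gives

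n = (2.5758 + 0.8416)² × (0.32×0.68 + 0.15×0.85) / 0.17² = 139.5, so 140 per arm, with power 0.8018.

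This agrees with the table in Section 9.2.1 (140 per arm, 0.80184).

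**2. The sign problem, by arithmetic.** Take illustrative differences of $500 and 5 points:

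- VIT dearer and worse: +$500 / -0.05 = -$10,000 per quit.
- VIT cheaper and better: -$500 / +0.05 = -$10,000 per quit.

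**3. Inputs for the simulation.** From the documents: EUC quit rate 15%, and 308 patients in total (Section 9.4), taken as 154 per arm. Assumed, because Section 6.4 names cost sources but no amounts: extra cost $600 per person with SE $30, and thresholds of $5,000 and $10,000 per quit. Cost and quit differences are drawn as independent normals, with SE(quit difference) = √{[p_V(1-p_V) + 0.15×0.85]/154}.

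**4. Test against zero.**

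- True effect 17 points: SE 0.0473, and the ratio's 95% range is about $2,250 to $7,780. It excludes zero because the cost difference does.
- True effect 5 points: SE = √[(0.16 + 0.1275)/154] = 0.0432, and the range is about -$105,000 to +$121,000, with a median near $9,400. The range contains zero, yet the cost difference is positive in every draw. The negative ratios all come from negative quit differences.

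**5. Threshold count.** Compare P(ratio < λ) with P(λ × quit difference - cost difference > 0), the probability of positive net benefit. When the extra cost is surely positive, the gap is the share of draws with VIT dearer and worse, Φ(-d/SE), where d is the true quit difference. At 5 points this is Φ(-0.05/0.0432) = Φ(-1.157) = 12.4%.

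| True effect | λ | Ratio below λ | Net benefit > 0 | Excess (points) |
|---|---|---|---|---|
| 17 points (design) | $10,000 | 99.0% | 99.0% | 0.02 |
| 10 points | $10,000 | 82.5% | 81.1% | 1.4 |
| 5 points | $5,000 | 17.7% | 5.4% | about 12 |
| 5 points | $10,000 | 53.2% | 40.9% | about 12 |
| 3 points | $10,000 | 47.8% | 23.9% | 23.9 |
| none | $10,000 | 57.0% | 7.1% | 50 |

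**6. Sensitivity to the assumed costs.** With extra cost $500 and a per-person SD of $400, the 5-point case at $10,000 gives 62.5% against 50.1%, again an excess of 12.4 points. With extra cost $200 (SD $400) the 5-point excess is still 12.4 points. With $1,000 (SD $800) the no-effect excess is still 50 points. The excess depends on the quit rates and the sample size, not on the dollar figures, as long as the extra cost is clearly positive.

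**The case against.** Four points can be made for the plan.

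**The threshold rule is unspecified, not wrong.** A reader might infer that the plan scores dearer-and-worse draws as cost-effective. The text does not say so. It speaks of simulation outcomes rather than ratios, and names no favourable side. Shares against several thresholds could even form an acceptability curve. This stands: the defect is a missing rule. The ratio is, however, the only statistic defined, so counting ratios is the natural way to carry the text out.

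**The draws contain the needed information.** A reader might infer that the analysis cannot separate the two kinds of negative ratio. Each draw carries its own cost and quit difference, so its quadrant is known. Only collapsing the pair into a ratio loses it. This also stands, and it makes the repair cheap.

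**The test against zero is not always a restatement of positive cost.** That description fits a clear effect. With a small effect and a surely positive cost, the ratio's sign is the sign of the quit difference, so the test reflects uncertainty about the effect. It is still not a test of cost-effectiveness.

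**The stakes are limited.** Cost is exploratory, Section 9.8.2 describes implementation outcomes mainly descriptively, and no trial decision depends on them. At a true 5-point effect the primary test has about 8% power with 154 per arm, Φ(0.05/0.0432 - 2.576), so the ratio would usually stand beside a non-significant result. This lowers the priority. The sensitivity analyses and best and worst cases do not settle how negative quit differences are classified.

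The average of the simulated ratios should not be used as evidence either way. The denominator has density at zero, so the average has no stable value: repeated runs at 5 points gave anything from about -$69,000 to +$18,500. The plan does not propose to report it.

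**Conclusion.** The concern holds in a limited form. The planned test against zero is in the text, does not address whether VIT is worth its cost, and is not repaired elsewhere. The treatment of draws with a negative quit difference is left open, and the natural reading would overstate the probability that VIT is cost-effective.

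The overstatement is negligible if the design effect is true. It becomes material only if the effect is small, null or reversed. These sizes rest on a 15% EUC quit rate, 154 per arm, normal approximations and an extra cost that is clearly positive. The threshold shares and the width of the ratio's range also depend on the assumed dollar amounts; the excess does not. The documents do not support saying that the plan has adopted a rule favouring dominated draws. Priority is modest because the outcome is exploratory.

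**What to change.** In Section 9.8.2.5:

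1. Delete the test of the ratio against zero.
2. From the same draws, compute incremental net monetary benefit: threshold × quit difference - cost difference.
3. State a range of thresholds per quit in advance, and report the probability that net benefit exceeds zero across it (an acceptability curve).
4. Show the cost-effect plane with the share of draws in each quadrant.
5. Keep the point estimate of incremental cost per quit as defined, with the planned sensitivity analyses.

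This needs new SAP wording and a little more analysis. It needs no new data and no change to the simulation. The one added demand is that the investigators commit to a threshold range.
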